3.3. Flowchart *

The flowchart of the proposed study is shown below. The patients have the option to choose the new biopsy with the 3D image guidance. All the imaging scans will be the same as the IRB-approved study (IRB00061518). We hypothesize that the 3D image-guided biopsy may be able to detect the cancer that was missed by the current biopsy with 2D image guidance.

* Estimates based upon Urologic experience at our institution

** Estimates of numbers in follow-up or biopsy categories based upon preliminary recurrence data

*** This represents positives on any one modality, not just FACBC scanning

**** Most high-risk patients will have positive imaging and are thus directed to the right hand side of the flowchart

Patients will undergo the usual clinical and presurgical evaluation with studies deemed necessary by the Urology team including pelvic CT, bone scanning. **Note that the PET scan will be part of the IRB-approved study (IRB00061518). Hence, this study will NOT involve radiation from PET scans.** Our study will focus on the feasibility test of the 3D image-guided biopsy with the aid from FACBC PET imaging. Six patients will participate in this study. Once the feasibility of the proposed biopsy is validated, the data from this pilot patient study will provide important data for a large study in the next phase.

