We hypothesize that FACBC molecular images can be incorporated into ultrasound-guided biopsy for improved cancer detection. This research is to test a molecular image-directed, 3D ultrasound-guided biopsy system. The specific aims include:

Aim 1: To test a real-time, mechanically assisted, 3D ultrasound-guided device

An FDA-approved mechanical device will be used to guide, track, and stabilize the position of an ultrasound probe. The device will be used to acquire 3D TRUS images, reconstruct a 3D model of the prostate, and record the biopsy core locations in three dimensions. Compared to conventional 2D image guidance, 3D images of the prostate will be used to guide the biopsy procedure.

Aim 2: To develop fast DSAM-based segmentation methods for 3D ultrasound images

This aim is to develop image processing and analysis methods for ultrasound images. A deformable and statistical appearance model (DSAM) of the prostate will be created from our TRUS image databases. The prior information from our DSAM model will be used to guide automatic segmentation of the prostate on 3D TRUS images. The new model-based segmentation method will improve the speed and accuracy and will save time during biopsy.

Aim 3: To combine FACBC PET images with 3D ultrasound for targeted biopsy

This aim is to develop image registration methods for PET/CT and ultrasound images. A new deformable registration method based joint saliency map (JSM) and fuzzy point correspondence (FPC) will be developed in order to combine FACBC PET/CT images with 3D ultrasound. Multimodality image fusion methods will be developed to incorporate FACBC images into ultrasound-guided biopsy in order to better locate suspicious tumors and thus improve needle guidance.

Aim 4: To test the accuracy of the integrated, molecular image-directed biopsy system

The accuracy of the integrated, multimodality image-directed biopsy system will be measured in phantoms and animal experiments. As our ongoing FACBC studies are recruiting human patients, the proposed FACBC-directed biopsy system will be tested in a small number of patients in order to lay the groundwork for large clinical trials using the new targeted biopsy technology.

3.0. Patient Selection:

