Forty-two (42) patients will be enrolled in this study. Patients who are enrolled in , IRB00061518 (PI: [name], Title: Transmolecular imaging of Recurrent Prostate carcinoma) and have a positive imaging scan will be scheduled for biopsy. These patients will be offered this study as an option instead of the 2D ultrasound biopsy.

The 3D ultrasound device has received the FDA 510K approval. Because the device can provide 3D ultrasound images as well as fused PET/MRI/ultrasound images, we think that the clinician will be able to better biopsy the tissue at the right location.

3.1. Inclusion Criteria:

[figure not shown]
- (1) Patients must be 18 years of age or older.
- (2) Abnormal uptake in prostate necessitating biopsy
- (3) Patients must be able to provide written informed consent.

3.2. Exclusion Criteria:

1. Age less than 18.
2. Cannot provide written informed consent.
3. Less than 2 months since any prior prostate biopsy (to decrease false positive uptake from inflammation).

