Patients who are prostate bed positive and extraprostatic negative will get treated with local therapy (radiation, cryoablation, salvage surgery, etc.) These patients will not get hormonal therapy and will be entered into the follow-up group. It is true that some patients with either high Gleason scores, impending or with cord compression and/or pathologic fracture, hydronephrosis, and/or rapid PSA doubling time of less than 3 months will require hormonal therapy, but this is not the majority of patients (approximately 15-20% worst case scenario). The majority of patients (80-85%) will have low to intermediate risk disease and PSA recurrence reflecting the prevalence of low and intermediate risk disease in the United States. Therefore these patients can be followed off hormonal therapy but with local therapy as needed.

9.0. Data Collection:

Form	Submission
Pre-registration	Prior to registration
Consent Form	
HIPAA Authorization	
Eligibility Form	
Baseline	
Registration Form	One the day of registration
During Scanning Protocol	
PET Imaging Findings Form	Within 7 days of completion of each diagnostic procedure

10.0. Statistical Considerations:

Although this pilot human study will not be able to provide the statistical power to analyze the sensitivity of the 3D image-guided biopsy, this small number of 6 patient study will be able to test the feasibility of the biopsy system and will provide important data for a large clinical trial later.

Reference

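### The pilot is to test feasibility and speaks of it being 'validated', but the protocol defines no per-patient feasibility outcome and no result that would count against it, and it gives two sample sizes (6 and 42).

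*Protocol*

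**What the plan says.** Section 3.3 sets the purpose of the human part: "Our study will focus on the feasibility test of the 3D image-guided biopsy with the aid from FACBC PET imaging". It adds "Six patients will participate in this study" and then links the result to what follows: "Once the feasibility of the proposed biopsy is validated, the data from this pilot patient study will provide important data for a large study".

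Section 10.0 sets sensitivity aside ("Although this pilot human study will not be able to provide the statistical power to analyze the sensitivity of the 3D image-guided biopsy") and in the same sentence affirms that "this small number of 6 patient study will be able to test the feasibility of the biopsy system".

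Aim 4, under Specific Aims, places accuracy elsewhere: "The accuracy of the integrated, multimodality image-directed biopsy system will be measured in phantoms and animal experiments". In patients, the system is to be "tested in a small number of patients in order to lay the groundwork for large clinical trials".

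Section 3.0 gives a different size: "Forty-two (42) patients will be enrolled in this study".

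Section 6.0 describes the procedure: PET/CT registered to 3D ultrasound, the needle guided to the suspicious lesion with real-time 2D images fused in, and the needle-tip position recorded after each core. The Section 9.0 table lists consent, authorization, eligibility and registration documents and a PET findings form.

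**The concern.** Once power for sensitivity is disclaimed, feasibility is the one question that Section 10.0 says the patients will answer. Answering it needs two things: an event that can be scored yes or no in each patient, and a result that would lead to the answer 'not feasible'. The protocol has neither. It also lists no form on which the evidence would be collected in a uniform way.

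This is not a detail that a protocol normally leaves to a statistical analysis plan. An interval method or an analysis set could wait for one. What the study is asking, and what would answer it, belongs in the protocol, and this protocol already asserts that the question can be answered.

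At stake is the only conclusion to be drawn from the patients. Without an outcome fixed beforehand, success can be defined after the results are known, and a later trial may be planned on a statement that no result could have contradicted. The conflict between 6 and 42 adds to this, because it changes how much even a perfect result would show.

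**Working it through.** **The text.** The places where a criterion could stand compare as follows.

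- Section 3.3: uses the word 'validated'; attaches no measure and no level.
- Section 10.0: says feasibility will be tested; gives no outcome, target rate or precision.
- Aim 4: accuracy is measured in phantoms and animals, with no tolerance; patients lay groundwork only.
- Section 6.0: lists steps that could be scored, but calls none of them a success or a failure.
- Section 9.0: no form for registration, targeting or biopsy results.

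**The plan's own figures.** Neither 6 nor 42 comes with an assumed rate, error level, power or precision, so there is no calculation to reproduce.

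**Inputs for the check.** n = 6 (Sections 3.3 and 10.0) and n = 42 (Section 3.0). Assumptions that the protocol does not state: a binary outcome per patient, a 95% level, exact (Clopper-Pearson) limits.

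**Best case, no failures.** The two-sided upper limit for the failure rate is 1 − 0.025^(1/n); the one-sided limit is 1 − 0.05^(1/n).

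| n | Two-sided | One-sided |
|---|---|---|
| 6 | 1 − 0.025^(1/6) = 45.9% | 39.3% |
| 42 | 1 − 0.025^(1/42) = 8.4% | 6.9% |

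With one failure, the two-sided limit is 64.1% at n = 6 and 12.6% at n = 42.

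**Intervals for the success proportion at n = 6.** 6 of 6 gives 54.1% to 100%; 5 of 6 gives 35.9% to 99.6%; 4 of 6 gives 22.3% to 95.7%.

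**Chance of a clean run of six when failures do occur.** (1 − f)^6 for a true failure rate f: 0.9^6 = 53% at f = 10%, 0.8^6 = 26% at 20%, 0.7^6 = 12% at 30%.

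**What an explicit rule would do.** For at least 5 successes in 6, with true success rate p, the chance of passing is 6p^5(1 − p) + p^6:

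- p = 0.5: 6/64 + 1/64 = 0.109
- p = 0.7: 0.3025 + 0.1176 = 0.420
- p = 0.9: 0.3543 + 0.5314 = 0.886

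For comparison, at least 34 successes in 42 passes with probability 0.080 at p = 0.7 and 0.979 at p = 0.9.

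**The case against.** The strongest reply is that this is a small, non-randomised diagnostic pilot of a cleared device, that it openly disclaims power, and that it speaks only of informing a later study. No decision-maker, automatic next phase or formal stopping rule is described. That is right as far as it goes: the Section 3.3 sentence is a loose progression condition, not a gate. A reader might infer that the pilot is bound to lead to a large trial whatever happens. The documents do not support that. With no rule, the chance of going on depends on judgement and cannot be computed. What stands is narrower: nothing in the protocol says which result would be unfavourable.

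A reader might also infer that six patients miss a promised precision. They do not, because the protocol promises none for a feasibility rate. A wide interval is inherent in a pilot of six, and more patients are not being asked for. The 45.9% shows what a perfect result would leave open. It applies only to n = 6, no failures and a two-sided 95% limit.

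The disclaimer in Section 10.0 does not meet the point, since it concerns sensitivity and the same sentence affirms the feasibility test.

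Finally, a rule of at least 5 in 6 is itself weak: a system that succeeds in 70% of patients would pass 42% of the time. That is true. It is a reason to print the operating characteristics beside the rule, not a reason to have none.

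**Conclusion.** The point holds and should be fixed, though it is not of the highest severity. The protocol presents feasibility as tested and possibly validated, without a per-patient outcome, a result that would count as not feasible, or a listed form to record the evidence. As written, the conclusion can be drawn from any outcome.

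Separately, the sample size contradicts itself (42 against 6) and must be reconciled. The two sizes differ greatly in what they can show: with no failures, the upper limit for the failure rate is 45.9% at 6 and 8.4% at 42. The documents do not settle which number is meant.

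The textual finding does not depend on the sample size. The percentages depend on the assumptions listed with the calculation. One caveat: the flowchart image in Section 3.3 was not available for this check. Its footnotes concern expected patient numbers and categories and point to no feasibility criterion.

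**What to change.** 1. Reconcile the number of patients across Sections 3.0, 3.3 and 10.0.
2. In Section 10.0, define technical success for each patient from the Section 6.0 steps: registration of PET/CT to 3D ultrasound completed at the visit, the PET-suspicious lesion cored under fused 3D guidance, and the core location recorded. Avoid defining failure as any use of 2D ultrasound, because Section 6.0 itself uses real-time 2D images. Say which patients form the denominator.
3. Add a biopsy form to the Section 9.0 table that records each of these items.
4. Pre-state the minimum number of successes for the reconciled sample size, with its operating characteristics. If six is kept, at least 5 of 6 is one example (11%, 42% and 89% chance of passing at true success of 50%, 70% and 90%). If 42 is kept, at least 34 of 42 would pass 8% of the time at 70% and 98% at 90%.
5. Report the success proportion with its exact 95% interval.
6. In Section 3.3, replace 'validated' with 'supported'.

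The cost is a few sentences and one extra form. Steps 2 to 6 need no extra patients. The downside is a more modest claim and a result that may turn out negative.

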4.1. Conventional Imaging Performance and Interpretation

All the conventional imaging performance and interpretation will be the same as those in the IRB-approved study (IRB00061518). Briefly, as part of the standard workup of suspected recurrent prostate cancer, all patients will have undergone standard evaluation which includes bone scan, pelvic CT with oral and IV contrast,. These are already obtained as part of our routine evaluation, and will not place an extra financial burden on the proposed study. Details on the imaging methods are described in the approved IRB protocol IRB 00061518.

5.0. Registration/Randomization:

Patients will be registered and consented into the study by one of the research nurses on staff working in the clinical Urology setting. There will be no randomization.

Patients who are prostate bed positive and extraprostatic negative will get treated with local therapy (radiation, cryoablation, salvage surgery, etc.) These patients will not get hormonal therapy and will be entered into the follow-up group. It is true that some patients with either high Gleason scores, impending or with cord compression and/or pathologic fracture, hydronephrosis, and/or rapid PSA doubling time of less than 3 months will require hormonal therapy, but this is not the majority of patients (approximately 15-20% worst case scenario). The majority of patients (80-85%) will have low to intermediate risk disease and PSA recurrence reflecting the prevalence of low and intermediate risk disease in the United States. Therefore these patients can be followed off hormonal therapy but with local therapy as needed.

9.0. Data Collection:

Form	Submission
Pre-registration	Prior to registration
Consent Form	
HIPAA Authorization	
Eligibility Form	
Baseline	
Registration Form	One the day of registration
During Scanning Protocol	
PET Imaging Findings Form	Within 7 days of completion of each diagnostic procedure

10.0. Statistical Considerations:

Although this pilot human study will not be able to provide the statistical power to analyze the sensitivity of the 3D image-guided biopsy, this small number of 6 patient study will be able to test the feasibility of the biopsy system and will provide important data for a large clinical trial later.

Reference

